9.6.1.7.3 Treatment of vomiting and diarrhea

Adequate hydration through appropriate fluid maintenance is essential for the treatment of diarrhea or vomiting. Anti-diarrhea medications may be introduced if symptoms occur. The recommended dose of loperamide is 4 mg at first onset, followed by 2 mg every 2 to 4 h until diarrhea-free for 12 h, a maximum daily dose of 16 mg is not to be exceeded. If clinically indicated diphenoxylate or Lomotil, which contains diphenoxylate plus atropine might also be used. The routine use of standard antiemetics, including 5-HT₃ blockers is allowed, see Section 8.1 for permitted concomitant therapy.

9.6.2 Pregnancies

A subject's participation is to be terminated immediately if a pregnancy is supposed (i.e. in case her pregnancy test becomes positive).

The investigator must report to the sponsor any pregnancy occurring in a female study subject during her participation in this study. The outcome of the pregnancy should be followed up carefully, and any outcome of the mother and the child at delivery should be reported.

For a pregnancy in the partner of a male study subject, all efforts will be made to obtain similar information on course and outcome, subject to the partner's consent.

For all reports, the forms provided are to be used. The investigator should submit them within the same timelines as an SAE.

9.6.3 Safety examinations

The following safety examinations will be performed at the time points specified in the study flowchart, see Section 16.1.

- **Physical examination**

The physical examination (by means of inspection, palpation, auscultation) will be performed by a physician at the study site according to the schedule summarized in the flow chart in Section 16.1.

Complete physical examination includes the NYHA classification (see Section 16.9) and complete reviews of body systems.

All clinical signs and regions that can be brought into context with the underlying disease, with the anti-cancer treatment to be administered or with relevant accompanying diseases (if present) should be clinically assessed.

At the minimum, the following aspects / regions need to be assessed as well:

- General appearance
- Skin (paleness, jaundice, redness / rash, acneiform changes)
- Hand and feet (signs of hand-foot syndrome / palmar-plantar erythrodysesthesia)
- Eyes (accommodation, double images, abnormal sensitivity to light, jaundice)
- Ears, nose, throat (presence of petechial bleedings, gingiva bleeding)
- Head and neck
- Lungs
- Heart
- Abdomen (pain, tenderness, peristaltic, ascites, organomegaly)
- Lymph nodes
- Musculoskeletal system and spine
- Lower legs (petechial bleedings, ulcer, signs of thrombosis)
- Neurologic findings

Abbreviated physical examinations will be performed (by inspection, palpation, and auscultation) by a physician at the study center according to the schedule summarized in the flow chart in Section 16.1.

Abbreviated physical examination includes pertinent organ systems and brief interim history (change of symptoms). At the minimum, the following aspects / regions need to be assessed as well:

- Skin (paleness, jaundice, redness / rash, acneiform changes)
- Hand and feet (signs of hand-foot syndrome / palmar-plantar erythrodysesthesia)
- Throat (presence of petechial bleedings, gingiva bleeding)
- Lungs
- Abdomen (pain, tenderness, peristaltic, ascites, organomegaly)
- Neurologic findings
- Other clinical signs and regions might be investigated as well if clinically indicated.

Abnormal physical examination findings are recorded either as medical history or as AEs (see Section 9.6.1.1).

- **Vital Signs**
 - Blood pressure (BP) / pulse rate (supine)

Systolic / diastolic blood pressure and pulse rate will be measured by a member of the investigator's team under the following conditions:

- Position: Supine (small pillow under head allowed) for at least 10 min
- Measuring site: cuff to be placed on the right / left upper arm (if possible, the same arm will be used for all measurements in one subject)
- Method: oscillometric by automatic measurement device

Body temperature, BP, and pulse rate will be assessed according to the schedule summarized in the flow chart in Section 16.1. If clinically indicated, it is at the investigator's discretion to perform these measurements more frequently.

BP will be measured every 5 to 10 min before the copanlisib dose until 2 consecutive values are <150/90 mmHg. A single BP measurement will be performed at the end of the copanlisib IV infusion.

For details about the management of arterial hypertension, see also Section 9.6.1.7.2 (treatment of arterial hypertension).

- **Body temperature**

Body temperature will be measured by a member of the investigator's team using always the same method according to local practice. The measured values are to be recorded in the electronic CRF in degree Celsius (°C).

- **Electrocardiogram**

A complete standard 12-lead ECG will be recorded by a member of the investigator's team under the following conditions:

- Position: supine (small pillow under head allowed) for at least 15 min
- Device: computerized ECG device
- Automatic calculation of the following parameters: RR interval, heart rate, P-duration, PR (PQ) interval, QRS-duration, QT (uncorrected). For data analysis by the sponsor, the frequency-corrected QT interval will be calculated according to both the formula of Fridericia (QTcF) and Bazett (QTcB) by data management.
- Evaluation of ECG by a physician providing an ECG diagnosis and overall assessment (including clinical relevance)

- **Laboratory examinations**

Blood and urine samples will be collected by a member of the investigator's team, for time points and parameters see Section 16.1 and Section 16.2 in the appendix.

The MDRD equation will be used for the eligibility assessment in Group B (see Section 16.5). The creatinine clearance will be calculated from the creatinine concentration measured in serum according to the Cockcroft-Gault formula after the study (see Section 16.6).

In the event of implausible results, the laboratory may measure additional parameters to assess the quality of the sample (e.g. clotted or hemolyzed) and to verify the results.

The results from such additional analyses may neither be included in the clinical database of this study nor evaluated further. If the results are relevant, the investigator will be informed to determine follow-up activities outside of this protocol.

9.7 Other procedures and variables

For virology and urine drug screen parameters and pregnancy test, please refer to [Table 16-2](#).

9.8 Appropriateness of procedures / measurements

All PK and safety parameters, as well as the methods to measure them, are standard variables/methods in clinical studies and/ or clinical practice. They are widely used and generally recognized as reliable, accurate and relevant.

10. Statistical methods and determination of sample size

10.1 General considerations

The statistical evaluation will be performed by using the SAS software package. All data will be listed and trial summary tables will be provided.

All data will be listed and study summary tables will be provided where appropriate. Quantitative data will be described by the following summary statistics: arithmetic mean, standard deviation, median, minimum and maximum. Whenever appropriate, summary statistics will be provided for the original data as well as for the change versus baseline. Graphical illustrations will be provided where appropriate. Frequency tables will be provided for qualitative data. Baseline is defined as the last pre-dose assessment before study drug administration.

10.2 Analysis sets

All subjects who received at least one dose of the study medication will be included in the safety analysis set (SAF).

All subjects with a PK profile allowing calculation of the main PK parameters will be included in the PK analysis set (PKS1).

All hepatically impaired subjects and gender, age- and weight-matched healthy subjects with a PK profile allowing calculation of the main PK variables will be included in the PK analysis set for hepatic impairment assessment (PKS2).

All renally impaired subjects and gender, age- and weight-matched healthy subjects with a PK profile allowing calculation of the main PK variables will be included in the PK analysis set for renal impairment assessment (PKS3).

10.3 Variables and planned statistical analyses - amended

Primary and secondary variables are specified in Section 5.

Statistical and analytical plans

- **Demographic and other baseline characteristics**

Analysis for population characteristics will be performed for the SAF population, unless otherwise specified.

Disposition at the end of screening will be summarized for all enrolled subjects. Disposition at the end of treatment will be summarized by group and overall for the SAF population.

Demographics will be summarized by group and overall. Quantitative data will be summarized by arithmetic mean, standard deviation, median, minimum and maximum. Frequency tables will be provided for qualitative data. Analysis of demographic data will also be performed for the PKS1 population if this population differs from SAF.

- **Adverse events**

Individual listings of AEs will be provided. The incidence of TEAEs and drug-related TEAEs, respectively, will be summarized by group and overall using MedDRA terms. Listings of deaths and SAEs will be provided.

Adverse events are considered to be treatment-emergent if they have started or worsened after first application of study medication up to 30 days after end of treatment with study medication.

- **Safety parameters**

Quantitative data for safety (hematology, clinical chemistry, coagulation, urinalysis, vital signs, ECG) will be described by descriptive statistics (arithmetic mean, standard deviation, median, minimum and maximum) and will be presented by each group for the original data as well as for the difference to baseline. Frequency tables will be provided for qualitative data.

Laboratory data outside the reference range will be listed and flagged with 'L' for low and 'H' for high.

Graphical displays of individual data as well as mean values with standard deviation will be included.

- **Pharmacokinetic variables**

The plasma concentration vs time courses of copanlisib (and its metabolite) will be summarized by group. The following statistics will be calculated for each plasma sampling point: arithmetic mean, standard deviation (SD) and coefficient of variation (CV), geometric mean, geometric standard deviation (re-transformed standard deviation of the logarithms) and CV, minimum, median, maximum value and the number of measurements. Means at any time will only be calculated if at least 2/3 of the individual data were measured and were above the lower limit of quantification (LLOQ). For the calculation of the mean value a data point below LLOQ will be substituted by one half of this limit. This rule also applies for means shown in figures. In tables showing mean values, where values below LLOQ are included in the calculation of mean values, these means will be marked.

Individual and mean concentration versus time profiles of all analytes will be plotted using both linear and semi-logarithmic scale.

Pharmacokinetic characteristics (t_{\max} and t_{last} excluded) will be summarized by the statistics mentioned above. T_{\max} and t_{last} will be described utilizing minimum, maximum and median as well as frequency counts.

To investigate the primary objective of this study regarding hepatic and renal impairment, analysis of variance appropriate for a parallel design will be fitted to the natural logarithmic transformation of PK parameters (AUC(0-168), AUC and C_{\max}) of copanlisib .

The test/reference comparison ratio of geometric least-squares means and associated 90% confidence intervals (CIs) for each PK parameter in the moderate hepatic, severe hepatic²⁹ or severe renal impairment group versus the matched healthy subjects group will be calculated by exponentiation of the natural-log scale point estimate and the associated 90% CI.

²⁹ Included as subjects with severe hepatic impairment will be included into the study according to Amendment 1

10.4 Determination of sample size - amended³⁰

The study population will consist of up to 44 evaluable male and female subjects with 8-22 evaluable subjects in the control group, 8 evaluable subjects each in the moderate hepatic and severe renal impairment investigational group, and 6 evaluable subjects in the severe hepatic impairment investigational group. The sample size of 8 subjects in each of the groups with impaired moderate hepatic and severe renal function and 6 subjects in the severe hepatic impairment group has been selected based on practical consideration and following the FDA guidance ^{[4][5]}.

In copanlisib studies 12871 and 16270, the SD for log-transformed AUC(0-168) or AUC was estimated between 0.33 and 0.40. For the current study, we assume the SD of 0.40 for log-transformed AUC(0-168). The PK parameter AUC(0-168) is considered appropriate for sample size estimation as in Study 16270 the extrapolation for calculation of AUC was only 4.8% of AUC(0-168). Further, based on the PK data from study 12871, the inter-subject variability for copanlisib PK exposure was estimated to be 46.5% for AUC(0-168) and 73.3% for C_{max} in terms of geometric coefficient of variation (CV). In study 16270, the inter-subject variability for C_{max} was 63.2% in terms of geometric mean CV. The AUC(0-168) value has been considered for sample size estimation as a suitable PK parameter because of the higher uncertainty around of the C_{max} especially for an i.v. drug. For AUC(0-168), a sample size of 8 eligible subjects each in the control, moderate hepatic and severe renal impairment investigational group would provide an approximately 90% chance for the 90% confidence interval for the ratio of geometric least-squares means between impaired subjects and healthy subjects to be within a 2-fold difference, that is, within limits of 50% to 200% for AUC(0-168). This can be shown in [Table 10-1](#) based on different observed ratios.

Table 10-1: 90% Confidence interval for copanlisib with N=8 per group - amended

Observed Ratio	90% CI for the ratio
1	(0.685, 1.461)
1.1	(0.753, 1.607)
1.2	(0.822, 1.753)
1.3	(0.890, 1.899)

A sample size of 6 eligible subjects per each in the control and severe hepatic impairment investigational group would provide an approximately 90% chance for the 90% confidence interval for the ratio of geometric least-squares means between impaired subjects and healthy subjects to be within an approximately 2-fold difference, that is, within limits of 50% to 207% for AUC(0-168) as shown in [Table 10-2](#) based on different observed ratios.

³⁰ Sample size determination revised as subjects with severe hepatic impairment will be included into the study according to Amendment 1

Table 10-2: 90% Confidence interval for copanlisib with N=6 per group - amended

Observed Ratio	90% CI for the ratio
1	(0.628, 1.593)
1.1	(0.691, 1.752)
1.2	(0.753, 1.911)
1.3	(0.816, 2.07)

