PROC GLM data=dataset;
```

```
CLASS group
```

```
MODEL log_PK = group;
```

```
LSMEANS group / pdiff cl alpha=0.1;
```

```
RUN;
```

Plots of the relationship between PK parameters of copanlisib and M-1 metabolite AUC(0-168), AUC, C_{max} , AUC(0-168)_u, AUC_u and $C_{max,u}$, respectively and eGFR (MDRD formula) and estimated creatinine clearance (Cockcroft-Gault formula) at screening.

Based on patient's age, weight and serum creatinine information collected at the visit, estimated creatinine clearance will be calculated as following:

for male, CL_{cr} (mL/minute) = $\{((140 - \text{age (years)}) \times \text{weight (kg)}) / (72 \times \text{Serum creatinine (mg/dL)})\}$;

for female, $CL_{Cr} \text{ (mL/minute)} = \{((140 - \text{age (years)}) \times \text{weight (kg)}) / (72 \times \text{Serum creatinine (mg/dL)})\} \times 0.85$.

The corresponding Spearman's rank correlation coefficients including the associated 95% confidence intervals will be calculated to explore any monotone relationship between the PK variables and eGFR at screening.

A linear regression analysis of PK variables versus eGFR at screening will be presented.

– Hepatic Impairment

To investigate the primary objective of this study regarding hepatic impairment, an explorative analysis of variance (ANOVA) including group as factor will be performed on the log-transformed values of PK parameters C_{max} , AUC, AUC(0-168). The factor group will have two levels (matched healthy subjects and moderate hepatic impaired subjects; or healthy subjects and severe hepatic impaired subjects). Point estimates (LS-Means) as well as 90% confidence intervals of the ratio

- Severe hepatic impaired group/ matched healthy volunteer group
- Moderate hepatic impaired group/ matched healthy volunteer group

will be calculated by retransformation of the logarithmic results given by the ANOVA.

A corresponding SAS code base is outlined above.

Plots of the relationship between PK parameters of copanlisib and M-1 metabolite AUC(0-168), AUC, C_{max} , AUC(0-168)_u, AUC_u and $C_{max,u}$, respectively and baseline hepatic function parameters (Child-Pugh Score, total bilirubin, prothrombin time, alpha 1-acid glycoprotein and albumin). The corresponding Spearman's rank correlation coefficients including the associated 95% confidence intervals will be calculated to explore any monotone relationship between the PK variables and baseline hepatic function parameters.

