The study population will consist of up to 44 evaluable male and female subjects with 8-22 evaluable subjects in the control group, 8 evaluable subjects each in the moderate hepatic and severe renal impairment investigational group, and 6 evaluable subjects in the severe hepatic impairment investigational group. The sample size of 8 subjects in each of the groups with impaired moderate hepatic and severe renal function and 6 subjects in the severe hepatic impairment group has been selected based on practical consideration and following the FDA guidance [3] [4]. In copanlisib studies 12871 and 16270, the standard deviation (SD) for log-transformed AUC(0-168) or AUC was estimated between 0.33 and 0.40. For the current study, we assume the SD of 0.40 for log-transformed AUC(0-168). The PK parameter AUC(0-168) is considered appropriate for sample size estimation as in Study 16270 the extrapolation for calculation of AUC was only 4.8% of AUC(0-168). Further, based on the PK data from study 12871, the inter-subject variability for copanlisib PK exposure was estimated to be 46.5% for AUC(0-168) and 73.3% for C_{max} in terms of geometric coefficient of variation. In study 16270, the inter-subject variability for C_{max} was 63.2% in terms of geometric mean CV. The AUC(0-168) value has been considered for sample size estimation as a suitable PK parameter because of the higher uncertainty around of the C_{max} especially for an i.v. drug. For AUC(0-168), a sample size of 8 eligible subjects each in the control, moderate hepatic and severe renal impairment investigational group would provide an approximately 90% chance for the 90% confidence interval for the ratio of geometric least-squares means between impaired subjects and healthy subjects to be within a 2-fold difference, that is, within limits of 50% to 200% for AUC(0-168). This can be shown in [Table 7-1](#) based on different observed ratios.

Table 7–1: 90% Confidence interval for copanlisib with N=8 per group

Observed Ratio	90% CI for the ratio
1	(0.685, 1.461)
1.1	(0.753, 1.607)
1.2	(0.822, 1.753)
1.3	(0.890, 1.899)

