A sample size of 6 eligible subjects per each in the control and severe hepatic impairment investigational group would provide an approximately 90% chance for the 90% confidence interval for the ratio of geometric least-squares means between impaired subjects and healthy subjects to be within an approximately 2-fold difference, that is, within limits of 50% to 207% for AUC(0-168) as shown in [Table 7–2](#) based on different observed ratios.

Table 7–2: 90% Confidence interval for copanlisib with N=6 per group

Observed Ratio	90% CI for the ratio
1	(0.628, 1.593)
1.1	(0.691, 1.752)
1.2	(0.753, 1.911)
1.3	(0.816, 2.07)

8. Document history and changes in the planned statistical analysis

- Approval of SAP v1.0 (25 Jul 2017)
- Final SAP v2.0 updated on 07 MAY 2018 according to the protocol amendment 1 forming integrated protocol Version 2.0, dated 28 Nov 2017
- Final SAP v3.0 updated on 25 JUL 2018 by adding the clearance creatinine calculation

9. References

- [1] d. 1. M. 2. Clinical Study Protocol BAY 80-6946 / 18041 Version 1.0.
- [2] V. 1. d. 1. D. 2. Clinical Pharmacology Standards (CLIPS).
- [3] d. a. a. i. o. d. a. l. M. 2. Guidance for Industry: Pharmacokinetics in patients with impaired hepatic function: study design.
- [4] d. a. a. i. o. d. a. l. M. 2. Guidance for Industry: Pharmacokinetics in patients with impaired renal function: study design.

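### The planning intervals use n−1 instead of 2n−2 degrees of freedom, and the 90% chance stated for six per group computes to about 77%

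*Protocol*

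**What the plan says.** Protocol 10.4 sets the planning variability: "For the current study, we assume the SD of 0.40 for log-transformed AUC(0-168". It says earlier studies gave log SDs between 0.33 and 0.40. It also says that in study 12871 "the inter-subject variability for copanlisib PK exposure was estimated to be 46.5% for AUC(0-168" as a geometric CV.

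Two tables follow, each giving the 90% interval at observed ratios of 1, 1.1, 1.2 and 1.3. Table 10-1 ("90% Confidence interval for copanlisib with N=8 per group - amended") is for eight per group and Table 10-2 for six. Each comes with a probability statement. For eight per group, the chance that the interval lies within 50% to 200% is put at about 90%. For six per group the text reads "A sample size of 6 eligible subjects per each in the control and severe hepatic impairment investigational group would provide an approximately 90% chance" and sets the range as "within limits of 50% to 207% for AUC(0-168", pointing to Table 10-2.

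SAP 7 repeats all of this in Table 7-1 ("90% Confidence interval for copanlisib with N=8 per group") and Table 7-2 ("90% Confidence interval for copanlisib with N=6 per group").

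The analysis itself is in Protocol 10.3 and SAP 6.3.1: a parallel-design ANOVA of the log PK parameter, with group at two levels (one impaired group against its matched controls). The SAS code is "MODEL log_PK = group", with no pair or block term.

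**The concern.** Two things do not fit together.

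- **Degrees of freedom.** The planned model estimates one pooled variance from two independent groups, so its error degrees of freedom are 2n−2. The tabulated intervals are wider than that model would give at SD 0.40.
- **The chance at six per group.** Going from eight to six per group raises the standard error by about 15% and costs degrees of freedom. Yet the stated chance stays at about 90% while the upper limit moves only from 200% to 207%. That small widening looked too little to compensate.

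These figures are the only quantitative statement of the precision the study will deliver on a primary variable. The study is meant to inform labelling, and the severe hepatic group is the smallest, so a reader needs to know how likely a clear answer is there.

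**Working it through.** **Inputs.** Log SD 0.40, n = 8 or 6 per group, limits 50–200% (N=8) and 50–207% (N=6), all from Protocol 10.4. Two-sided 90% intervals from Protocol 10.3. Unpaired two-level group model from SAP 6.3.1. The documents state no true ratio for the chances; 1 is assumed, the most favourable of the tabulated ratios.

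**Step 1: reproduce the printed intervals.** Interval = ratio × exp(± t × SE), with SE = 0.40 × √(2/n).

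- N=8: SE = 0.2000. With t(0.95, 7 df) = 1.8946 the half-width is 0.3789, so ratio 1 gives (0.685, 1.461), as printed.
- N=6: SE = 0.2309. With t(0.95, 5 df) = 2.0150 the half-width is 0.4654, so ratio 1 gives (0.628, 1.593) and ratio 1.3 gives (0.816, 2.070), as printed.

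All 16 limits match to the printed digits. Neither the normal quantile nor t on 2n−2 degrees of freedom reproduces them. The SE is the unpaired one, so only the quantile is wrong.

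**Step 2: use the degrees of freedom of the planned model.** t(0.95, 14) = 1.7613, half-width 0.3523. t(0.95, 10) = 1.8125, half-width 0.4186.

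| Observed ratio | N=8 printed | N=8, 14 df | N=6 printed | N=6, 10 df |
|---|---|---|---|---|
| 1 | 0.685, 1.461 | 0.703, 1.422 | 0.628, 1.593 | 0.658, 1.520 |
| 1.1 | 0.753, 1.607 | 0.773, 1.565 | 0.691, 1.752 | 0.724, 1.672 |
| 1.2 | 0.822, 1.753 | 0.844, 1.707 | 0.753, 1.911 | 0.790, 1.824 |
| 1.3 | 0.890, 1.899 | 0.914, 1.849 | 0.816, 2.07 | 0.855, 1.976 |

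Overstatement of the log half-width: 1.8946/1.7613 = 1.076 (7.6%) and 2.0150/1.8125 = 1.112 (11.2%).

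The 207% in the six-per-group sentence equals the upper limit of the last N=6 row. With 10 degrees of freedom that row ends at 1.976.

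**Step 3: compute the chances.** Chance = P(lower limit ≥ lo and upper limit ≤ hi). The log difference is distributed N(0, SE²) and the pooled variance as 0.40² × χ²(2n−2)/(2n−2). This was integrated numerically and checked with 1,000,000 simulated trials.

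| Comparison | Limits | Stated | Computed |
|---|---|---|---|
| 8 v 8, 14 df | 0.50–2.00 | about 90% | 90.0% |
| 6 v 6, 10 df | 0.50–2.07 | about 90% | 77.4% |
| 6 v 6, 10 df | 0.50–2.00 | – | 74.8% |

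The method returns the plan's own figure for N=8, so the fault lies in the N=6 statement. A 90% chance with 6 v 6 would need limits of about 0.44 to 2.27.

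**Step 4: sensitivity.**

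- Other calculations for 6 v 6 within 0.50–2.07 at SD 0.40 also fall short of 90%: normal quantile with known SD 84.6%, Welch 76.2%, paired 68.4%.
- Requiring only the upper limit gives 90.0%, but the text requires both limits.
- True ratio 1.1, 1.2 or 1.3: 75.3%, 67.9% or 57.7% (0.50–2.07).
- SD 0.33: 93.0% (0.50–2.07) or 91.7% (0.50–2.00).
- A CV of 46.5% is a log SD of √ln(1 + 0.465²) = 0.442. The N=6 chance is then 65.3% or 62.2%. With the correct degrees of freedom, N=8 at ratio 1 is (0.677, 1.476) and N=6 at ratio 1.3 is (0.818, 2.065).
- Six severe hepatic subjects against the minimum of eight controls (12 df, SD 0.40): 85.2% (0.50–2.07) or 83.1% (0.50–2.00). Ratio 1.3 gives (0.885, 1.911).

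**The case against.** The strongest reply is that nothing turns on these figures. The group sizes are said to rest on practical grounds and regulatory guidance, the SAP disclaims any confirmatory analysis, and the SAS procedure will apply the correct degrees of freedom to the reported intervals. All of that stands, and it makes the degrees-of-freedom slip on its own a tidy-up.

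The second reply is that 6 v 6 may not be the comparison actually made. Matching is on group means and at least eight controls are required. With 12 controls the chance within 0.50–2.07 would be 91.9%. This is fair, and the real shortfall may prove smaller than 13 points. But the sentence specifies six controls and is wrong on its own terms. The guaranteed minimum of eight controls still does not reach 90%, and more controls are permitted, not assured.

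Third, the 90% for eight per group also depends on a true ratio of 1 and SD 0.40; it is 65.5% at a true ratio of 1.3. That is right. The figure is correct under those conditions, but the plan does not state them.

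Finally, the plan does show lower precision at six per group, through wider intervals and a 207% limit. That softens the impression, but the equal 90% remains false.

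**Conclusion.** The concern holds. All eight intervals in each document use n−1 instead of 2n−2 degrees of freedom, which widens them by 7.6% (N=8) and 11.2% (N=6) on the log scale. This is conservative at SD 0.40.

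The more important error is the chance stated for six per group. It is 77.4% within 50–207%, or 74.8% within 50–200%, not about 90%. This rests on 6 v 6, SD 0.40, a true ratio of 1 and the planned unpaired model. It is sensitive to the SD: about 65% at 0.442 and 93% at 0.33 for the 50–207% limits. The N=8 chance is correct under the same assumptions.

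The correction should be made, but it does not affect the validity of the analysis.

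**What to change.** Make both corrections in one edit, in Protocol 10.4 and SAP 7.

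1. Replace the intervals in Protocol Tables 10-1 and 10-2 and SAP Tables 7-1 and 7-2 with the 14 df and 10 df columns above. Add to the captions: *SD 0.40 on the log scale, t on 14 df* (N=8) or *t on 10 df* (N=6).
2. Reword the six-per-group sentence to state *about 75% chance of lying within 50% to 200% (true ratio 1, SD 0.40, 6 subjects per group)*. If 207% is kept, the figure must be about 77%, but 207% would then match no row of the corrected table, so the 200% version is cleaner.
3. Do not change 207% to 200% while leaving the 90%: that would move the statement further from the truth (74.8%).
4. The N=8 percentage stays. Adding the same conditions (true ratio 1, SD 0.40) there would be a useful option.

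The cost is two tables and one sentence in each document. There is no operational cost and no change to group sizes or analysis.

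### The roughly 90% chance stated for the severe hepatic comparison with 6 per group is 75% to 77% under the plan's own assumptions

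*Protocol*

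**What the plan says.** Protocol section 10.4, repeated in SAP section 7, makes two parallel claims about the 90% confidence interval for the ratio of geometric least-squares means of AUC(0-168), impaired over healthy.

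- **Moderate hepatic and severe renal groups:** "a sample size of 8 eligible subjects each in the control, moderate hepatic and severe renal impairment investigational group would provide an approximately 90% chance" that the interval lies within 50% to 200%.
- **Severe hepatic group (Group C):** "A sample size of 6 eligible subjects per each in the control and severe hepatic impairment investigational group would provide an approximately 90% chance" that the interval lies "within limits of 50% to 207% for AUC(0-168").

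Both rest on one variability assumption: "For the current study, we assume the SD of 0.40 for log-transformed AUC(0-168"). This is the top of the range seen before, since "the SD for log-transformed AUC(0-168) or AUC was estimated between 0.33 and 0.40" in two previous studies. Each claim is followed by a table of confidence intervals for observed ratios of 1 to 1.3 (Tables 10-1 and 10-2 in the protocol, 7-1 and 7-2 in the SAP). The true ratio that the chance refers to is not given.

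SAP section 6.3.1 specifies the analysis as an ANOVA on log-transformed values with group as a two-level factor, so each comparison uses a variance pooled over two groups.

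**The concern.** The same chance of about 90% is claimed for 6 per group as for 8 per group, at the same SD, with the upper limit moved only from 200% to 207%. Going from 8 to 6 per group raises the standard error by about 15% and cuts the degrees of freedom from 14 to 10. Such a small change in one limit is unlikely to make up for that.

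The tables do not settle the matter. They show the interval that would follow from a given observed ratio with the SD taken as exactly 0.40. They do not show how often the interval will fall inside the limits.

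At stake is how precise the Group C comparison is said to be. Group C was added by Amendment 1 after a regulator's comment. Its results go into the final report agreed with the regulator, and the protocol's rationale says the study will guide labeling. Readers of section 10.4 would expect this comparison to be as well supported as the other two.

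**Working it through.** **Inputs**

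- SD of log AUC(0-168): σ = 0.40 (Protocol 10.4, SAP 7).
- Group sizes: 8 and 8, or 6 and 6 (same sections).
- Two-sided 90% interval, 5% per side (Protocol 10.3, SAP 6.3.1).
- Two-group ANOVA, residual df = n1 + n2 − 2 (SAP 6.3.1).
- True ratio: not stated. It is taken as 1, and values up to 1.3 are shown below.

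**Formula**

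The log-ratio estimate d is normal with mean ln(true ratio) and SE = σ·√(1/n1 + 1/n2). The interval is d ± t(0.95, df)·s·√(1/n1 + 1/n2), where s is the pooled SD and df·s²/σ² is chi-square with df degrees of freedom. The wanted figure is the probability that the lower end exceeds ln(0.50) and the upper end is below ln(2.00) or ln(2.07). It is averaged over the distribution of s by numerical integration.

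**Step 1: reproduce the plan's 8-per-group figure**

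SE = 0.40·√(2/8) = 0.200, df = 14, t = 1.761, limits 50% to 200%. Result: **90.0%** (1,000,000 simulations: 90.1%). The plan's 8-per-group figure reproduces, which supports both the method and a true ratio of 1.

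**Step 2: the same calculation for 6 per group**

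SE = 0.40·√(2/6) = 0.231, df = 10, t = 1.812.

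| Limits | Stated | Integration | Simulation |
|---|---|---|---|
| 50% to 207% | about 90% | **77.4%** | 77.4% |
| 50% to 200% | – | **74.8%** | 74.8% |

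A hand check holds s at exactly 0.40. For 50% to 207%, d must lie between −0.693 + 1.812·0.231 = −0.275 and 0.728 − 1.812·0.231 = 0.309. These are −1.19 and 1.34 standard errors, and the probability between them is 79.2%. Sampling variation in s lowers this to 77.4%.

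**Step 3: can another reading give 90%?** (6 per group, σ = 0.40, true ratio 1 unless stated)

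| Reading | 50% to 207% | 50% to 200% |
|---|---|---|
| Known variance (normal quantile) | 84.6% | 82.5% |
| s fixed at 0.40, t on 10 df | 79.2% | 76.6% |
| True ratio 1.1 | 75.3% | 71.4% |
| True ratio 1.2 | 67.9% | 63.0% |
| True ratio 1.3 | 57.7% | 52.3% |

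- Limits symmetric about 1 (1/2.07 to 2.07): 80.0%.
- With the lower limit held at 50%, no upper limit gives 90%; the ceiling is 87.4%. Symmetric limits would have to widen to about 44% to 227%.
- 90% is reached at σ of about 0.347 (50% to 207%) or 0.339 (50% to 200%). The plan assumes 0.40.
- Testing the upper limit alone against 207% gives 90.0%, but that reading gives 95.0% for 8 per group against 200%, so it does not explain both claims.

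**Step 4: more than 6 controls** (6 severe hepatic subjects, σ = 0.40, true ratio 1)

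| Controls | 50% to 207% | 50% to 200% |
|---|---|---|
| 8 | 85.2% | 83.1% |
| 12 | 91.9% | 90.5% |
| 22 | 96.4% | 95.6% |

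**Where the 207% limit appears**

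207% is also the upper end of the 1.3 row in Table 10-2. That row, (0.816, 2.07), reproduces with t on 5 df: 1.3·exp(2.015·0.231) = 2.07. On the 10 df of the planned ANOVA it would be (0.855, 1.976). Table 10-1 likewise reproduces on 7 df and not on 14. This is a separate inconsistency, but it bears on whether 207% is the right limit to quote.

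**The case against.** The strongest case is about consequence, not arithmetic.

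- **No decision hangs on the figure.** Section 10.4 says the sizes were chosen on practical grounds and following guidance. SAP sections 4.1 and 6.3.1 say that no confirmatory analysis is intended. The limits appear only in the sample-size text and are not a pass/fail rule anywhere. This stands, and it limits the severity: correcting the figure changes no estimate, analysis set or group size.
- **Group C will probably not be compared with only 6 controls.** The plan requires at least 8 controls valid for PK and allows up to 22. With 8 the chance is 83% to 85%, and it passes 90% with 11 controls (50% to 207%) or 12 (50% to 200%). This stands in part. The text nevertheless states 6 per group, the comparison is with matched controls, and neither document says how many will be matched to Group C. The maximum of 22 equals 8 + 8 + 6, which is compatible with 6.
- **The figure may refer to the upper limit only.** That reading does give 90.0%. It fails because the text names both limits, and because the same reading would make the 8-per-group figure 95.0%.

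How the 90% for 6 per group came about cannot be told from the documents.

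**Conclusion.** The statement is wrong as written in Protocol 10.4 and SAP 7. For 6 against 6, log-scale SD 0.40, a pooled two-group analysis and a true ratio of 1, the chance is 77.4% for 50% to 207% and 74.8% for 50% to 200%, not about 90%. With no true effect, the chance that the interval strays outside the stated range is 23% to 25% instead of 10%. A true ratio of 1 is close to the most favourable value for the plan, and at 1.3 the chance falls to 57.7% (50% to 207%). No two-sided reading at SD 0.40 reaches 90%.

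The error misstates the precision of one comparison. It does not invalidate the sample size, which was not derived from this probability, and the 8-per-group claim is correct at a true ratio of 1.

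**What to change.** In Protocol 10.4 and SAP 7, replace the chance stated for 6 per group with about 77% for 50% to 207% (about 75% for 50% to 200%), and say that it assumes a true ratio of 1 and an SD of 0.40. Add the same true-ratio assumption to the 8-per-group sentence, whose figure can stay.

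It would also help to say how many matched controls Group C will have. If that is 8, the figures to quote are about 85% and 83%.

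When making the change, check the degrees of freedom behind both interval tables, because the 207% limit matches a table entry computed on 5 df, not on the 10 df of the planned analysis.

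The cost is a wording change in two documents and a less favourable stated figure. No extra subjects and no change to the analysis are needed.
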